7. SPECIMEN COLLECTION PROCEDURES

Blood samples will be obtained per institutional protocol and assayed in local laboratory facilities as defined in **Section 6**.

8. ADVERSE EVENT CRITERIA AND REPORTING

This study will be using the descriptive terminology developed by the National Cancer Institute for use in reporting adverse events: Common Toxicology Criteria for Adverse Events (CTCAE) version 4.0, dated May 28, 2009. The CTCAE includes a grading (severity) scale for each adverse event term. Grades were developed using the following guidelines:

Grade 1: Mild; asymptomatic or mild symptoms; clinical or diagnostic observations only; intervention not indicated.

Grade 2: Moderate; minimal, local or noninvasive intervention indicated

Grade 3: Severe or medically significant but not immediately life-threatening; hospitalization or prolongation of hospitalization indicated; disabling; limiting self care ADL.

Grade 4: Life-threatening consequences; urgent intervention indicated.

Grade 5: Death related to AE.

In general adverse events will be reported as diseases or syndromes whenever possible, instead of reporting individual component symptoms, signs, laboratory abnormalities or sequelae.

8.1 Definitions

Adverse Event (AE) – For this study, it shall be defined as any untoward or unfavorable medical occurrence in a human subject requiring medical intervention (grade 2 or above) and outside of standard treatment for their underlying illness (i.e. sickle cell disease), including any symptom, or disease state, temporally associated with the subject's participation in the research, whether or not considered related to the subject's participation in the research

Serious Adverse Event (SAE) – Any adverse event temporally associated with the subject's participation in research that meets any of the following criteria:

- results in death;
- is life-threatening (places the subject at immediate risk of death from the event as it occurs);
- requires inpatient hospitalization or prolongation of existing hospitalization (not including usual sickle cell disease pain crises);
- results in a persistent or significant disability/incapacity;
- any other adverse event that, based upon appropriate medical judgment, may jeopardize the subject's health and may require medical or surgical intervention to prevent one of the other outcomes listed in this definition

Unexpected Adverse Event – Any adverse event occurring in one or more subjects in a research protocol, the nature, severity, or frequency of which is not consistent with either:

- the known or foreseeable risk of adverse events associated with the procedures involved in the research that are described in (a) the protocol-related documents, such as the IRB-approved research protocol or the current IRB-approved informed consent document, and (b) other relevant sources of information, such as product labeling and package inserts; or
- the expected natural progression of any underlying disease, disorder, or condition of the subject(s) experiencing the adverse event and the subject's predisposing risk factor profile for the adverse event.

Unanticipated problem involving risks to subjects or others (UP): Any incident, experience, or outcome that meets all of the following criteria:

- unexpected (in terms of nature, severity, or frequency) given (a) the research procedures that are described in the protocol-related documents, such as the IRB-approved research protocol and informed consent document; and (b) the characteristics of the subject population being studied;
- related or possibly related to a subject's participation in the research; and

- suggests that the research places subjects or others at a greater risk of harm (including physical, psychological, economic, or social harm) related to the research than was previously known or recognized.

Attribution – the determination of whether an adverse event is related to a transfusion procedure.

Attribution categories:

1. Not Related - Event clearly related to other factors (e.g., clinical state, other therapies; concomitant drugs)
2. Possibly Related - Sequence of event is compatible with study drug, device, or procedure, but could have been produced by other factors
3. Probably Related - Sequence of event is compatible with study drug, device, or procedure and cannot be explained by other factors without much doubt
4. Definitely Related - Sequence of event is compatible with study drug, device, or procedure and beyond doubt cannot be explained by other factors

8.2. Types of Adverse Events to be Collected

Specific information about the following events will be collected for this study on the adverse event checklist case report form:

1. Serious adverse events, regardless of attribution to red cell transfusion
2. Specific adverse events, regardless of attribution to red cell transfusion
 - Myocardial infarction
 - Pulmonary embolism
 - Stroke
 - Renal failure or acute injury
 - Infection/sepsis
 - Ventricular tachycardia
 - Ventricular fibrillation
 - Transfusion-associated congestive heart failure/transfusion-associated circulatory overload (TACO)
 - Transfusion-related acute lung injury (TRALI)
 - Anaphylaxis
 - Graft vs. Host Disease (GVHD)
 - Grade 2 (medical intervention needed) or higher events of the following types:
 - Allergic reaction
 - Sinus bradycardia
 - Sinus tachycardia
 - Hypertension
 - Hypotension
 - Dyspnea
 - Hypoxia

- Wheezing
- Fever
- Hemolysis
- Hyperbilirubinemia
- Hemoglobinuria.

3. Unexpected adverse events (all grades), attributed as possibly, probably or definitely related to red cell transfusion

4. Unanticipated problems

8.3. Timeline for Reporting of Adverse Events

Study staff must fill out an Adverse Event Checklist form within 7 days of each randomized transfusion. The Adverse Event Checklist will indicate whether or not one or more of the events listed in Section 8.2 occurred during the transfusion. The PI will be also be notified of the identified event within 24 hours of learning of the event by phone or email.

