Patient Sample Processing: Blood will be obtained by port or peripheral access as available. Patient white cells will be isolated with established Ficoll separation techniques.. White cells will be tested by flow cytometry as above for key markers of activation (macrophages: CD62L, CD64, CD80, CD86, Tim1, neutrophils: The plasma fraction from each sample will be diverted to EPR (Bruker Elexys X-band system, Billerica, MA, USA), a Bio-Plex cytokine assay kit (Bio-Rad Laboratories), and a fluorescent immunoassay (DxFerr kit) to measure concentrations of free heme/hemoglobin, cytokines (IL-1, IL-6, IL-8, MCP-1), and NTBI, respectively. Clinical measurements obtained from patients will also include: CBC (4ml EDTA), reticulocyte count (4ml EDTA), HbS% (3ml EDTA), haptoglobin (1ml red top), chemistry labs (ferritin (0.5ml red top), iron saturation (1ml red top), lactate dehydrogenase (1ml red top)), urinalysis (12 ml) and blood culture (8-10ml/bottle). These clinical labs will be measured at intervals specifically defined in **Table 1**. Individual human samples of plasma and RBC will also be sent to [name] at the University of Colorado Denver to measure lipid metabolites and metabolomic profiles pre vs. post transfusion as an additional exploratory goal of this trial. The laboratory of [name] and his representatives will be receiving 30-200 individual samples of plasma and RBCs for this purpose. All samples will be de-identified.

6.3 Patient Clinical Outcomes:

A daily pain diary will be used and subjects will rate their pain on a ordinal numeric pain rating scale (0-10), indicate whether the pain was consistent with a “crisis,” indicate whether they utilized a healthcare facility, and record the amount of opioids used. Infection symptoms will also be documented daily along with the type, duration, and dose of any antibiotics taken if applicable. Subject ED and hospitalization events, and etiologies (see *definitions in 6.7*), will be recorded at regular intervals by the study coordinator during the study period using the available electronic medical record. Of note, diary completeness will be assessed at each face-to-face visit.

6.4 Patient Physical Exam:

Prior to each randomized transfusion, the PI or appropriately trained designee will perform a basic assessment of the patient. This exam will include a basic interval history (including review of any ED or hospital visits), a focused review of systems, and a focused physical exam.

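### Section 8.3 limits the adverse event checklist to events during the transfusion, against Sections 8.1 and 8.2, and later events found by other routes have no stated path into the AE log

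*Combined protocol and SAP*

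**What the plan says.** Section 8.1 defines an adverse event by its link to the study: it is "temporally associated with the subject's participation in the research, whether or not considered related" to that participation. The SAE definition uses the same link. Neither definition is confined to the hours of a transfusion.

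Section 8.2 names the form: "Specific information about the following events will be collected for this study on the adverse event checklist case report form". Its first two groups are "Serious adverse events, regardless of attribution to red cell transfusion" and "Specific adverse events, regardless of attribution to red cell transfusion". The second group includes infection or sepsis, stroke and GVHD. It also includes fever, hemolysis and hyperbilirubinemia at grade 2 or higher. Unexpected events judged at least possibly related, and unanticipated problems, complete the list.

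Section 8.3 sets the form's deadline and its content: "Study staff must fill out an Adverse Event Checklist form within 7 days of each randomized transfusion", and "The Adverse Event Checklist will indicate whether or not one or more of the events listed in Section 8.2 occurred during the transfusion".

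Other sections record clinical events without that limit:

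- **Diary (6.3):** "Infection symptoms will also be documented daily along with the type, duration, and dose of any antibiotics taken if applicable".
- **Medical record (6.3):** the coordinator extracts ED and hospital events, with causes, throughout the study period.
- **Interval history and exam (6.4):** done before each randomized transfusion.
- **Final assessment (synopsis):** four weeks after the last transfusion.

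Under Sections 8.4 and 8.6 the DSMB meets yearly. It receives AE logs and SAE reports for each subject and looks by arm at SAEs and at infections leading to ED or hospital care.

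**The concern.** A coordinator who follows 8.3 literally would leave a listed event off the checklist if it began an hour after the unit finished. One who follows 8.1 and 8.2 would enter it. The protocol runs at more than one site, so the two readings could produce safety data that are not comparable.

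The trial's own hypothesis concerns what happens after an older unit is given. The Aim 3 primary outcome is post-transfusion infection, and the blood schedule looks for hemolysis and immune activation hours later. A safety form confined to the transfusion does not match that hypothesis. At stake is the completeness of the AE log from which the DSMB judges the two arms.

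**Working it through.** The plan states no figure on this point, so there is none to reproduce. The check sets the sections side by side.

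**1. Does the limit in 8.3 reach the whole list?** Yes. 8.2 places its events on the checklist, and 8.3 describes that same checklist and refers to the events of 8.2 without exception. The list has 11 named conditions and 12 event types at grade 2 or higher, so 11 + 12 = 23 specific types, plus SAEs, unexpected events and unanticipated problems. The limit therefore covers SAEs as well as minor events.

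**2. When could the trial's own contacts reveal a later event?** Timings come from 6.2, the chronic transfusion schedule in 6.8 and the synopsis.

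| Contact | Time after transfusion | Relative to the 7-day filing deadline |
|---|---|---|
| 2-hour sample | 1.5 to 3 hours | before |
| 24-hour sample | 21 to 27 hours | before |
| 2-week sample | day 14 ± 2, so day 12 to 16 | 12 − 7 = 5 days after, at the earliest |
| Next transfusion visit | 3 to 8 weeks, so day 21 to 56 | 21 − 7 = 14 to 56 − 7 = 49 days after |
| Final assessment (after the third transfusion) | day 28 | 28 − 7 = 21 days after |

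Every contact falls after the transfusion. Three of the five fall after the form is due, and no section provides for updating it. The 7 days are a filing deadline, not an observation window. They are used here only to show that an update rule is needed.

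**3. Which later events have another route?**

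| Later event | Where it is recorded | Stated path onto the AE form or log |
|---|---|---|
| Infection | diary, medical record, interval history; Aim 3 outcome | none, but the DSMB sees those leading to ED or hospital care |
| Listed event seen in ED or hospital | medical record, interval history | none stated |
| Death, or SAE judged at least possibly related | 8.4: PI notification and DSMB chair | yes, once reported |
| Non-fatal SAE judged unrelated | medical record if seen in ED or hospital | none; the checklist is the only form 8.2 names |
| Grade 2 hemolysis on the 24-hour sample | haptoglobin, plasma hemoglobin and LDH results | none stated |
| Outpatient grade 2 fever or hyperbilirubinemia | possibly interval history; diary if fever comes with infection | none stated |

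**4. What feeds the AE log?** 8.6 sends the log to the DSMB, and 8.4 has all adverse events reviewed at the yearly call. No section says that diary, record-review, interval-history or laboratory findings are transferred to it.

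**5. When does collection end?** No start or end date for AE or SAE collection is given. Section 6.7 lists completion of the three transfusions as an end of participation, while the synopsis assesses subjects four weeks later. The period after the third transfusion is therefore unclear.

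**The case against.** The strongest reply is that the phrase in 8.3 is loose drafting and little would be lost in practice. Infection, the harm of most interest, is an Aim 3 outcome with daily diary recording and prescribed antibiotics in its definition. ED and hospital events come from the medical record for the whole study. An interval history, review of systems and exam precede each randomized transfusion. The DSMB compares SAEs by arm with no relatedness or time limit, and 8.5 sends all adverse events to the IRB under institutional policy. No section says that the DSMB tables are built from the checklist alone.

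Much of this stands. A reader might infer that delayed events on the list are lost altogether, or that the DSMB would see almost none of them. The routes above rule that out, most clearly for infection. A reader might also infer that the form is closed after 7 days, but the documents are silent on reopening it. Nor can the share of calendar time covered by the form serve as the share of events missed.

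Table 1 has an AE assessment row whose cells are blank in the available text. The physical exam row is blank too, although 6.4 schedules that exam, so the marks may have been lost. The row is evidence for neither side.

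The reply does not remove the conflict between 8.1, 8.2 and 8.3, and it points to no sentence that carries findings from the other routes into the AE log.

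**Conclusion.** The point holds as an internal contradiction with a bounded consequence. Following 8.3 as worded keeps listed events that start after the transfusion off the only AE form that 8.2 names. Those without a stated path onto it are chiefly non-serious events managed outside ED and hospital, together with non-fatal SAEs judged unrelated.

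The number of such events cannot be estimated, because the documents give neither their frequency nor the usual delay before the listed conditions appear. Calling any particular condition delayed is an assumption. The wording is the same for both arms, so the documents support a loss of safety information, not a bias toward one arm. Nothing in Section 10 ties the Aim 1 to 3 primary outcomes to the checklist.

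The conclusion assumes that staff would apply 8.3 literally and that no CRF instruction outside these documents already widens the window.

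**What to change.** Make four changes:

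1. In 8.3, have the checklist record listed events that occurred since the start of that study transfusion.
2. Have the checklist updated at contacts already scheduled: 24 hours, 2 weeks, the next pre-transfusion visit, and the assessment four weeks after the last transfusion.
3. State that listed events found by diary, record review or interval history are transferred to the AE log, so that the log sent to the DSMB has a defined source.
4. Reconcile Section 6.7 with the four-week assessment in the synopsis, so that the end of AE and SAE collection is explicit.

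The cost is one revised sentence, a short addition on transfer to the log, a wording change on the CRF and slightly more data entry. No new visit or sample is needed.

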8.4. Review of Events for Subjects Enrolled

The Data Safety Monitoring Board (DSMB) is an independent board appointed by the PI. The principal role of the DSMB is to regularly monitor the data from the clinical trial, review and assess the performance of its operations, and make recommendations, as appropriate, to the PI and IRB.

The PI will be notified within 24 hours of learning of an event when a serious adverse event possibly, probably or definitely related to red cell transfusion or an event resulting in death (regardless of attribution) is reported. The PI will review the event as soon as the materials are available. The PI may request additional information regarding the event and may request the subject's treatment arm assignment. Following the review, the PI will sign a log summarizing the event.

The DSMB chairperson will receive information on all serious adverse events possibly, probably, or definitely related to red cell transfusion and all events resulting in death (regardless of attribution). The DSMB chair has expertise in benign hematology and transfusion medicine, will review the serious adverse event materials, and determine if the information is complete.

The DSMB members will meet annually via teleconference. All adverse events will be reviewed during the call, and the group will vote if additional DSMB review is required, and make recommendations about the study.

8.5. Reporting Events to Local Institutional Review Boards

The investigator will notify the local Institutional Review Board (IRB) of all adverse events in accordance with institutional policy.

8.6. Annual DSMB Reports

The DSMB will meet once a year, either in-person or via teleconference. The PI will provide the DSMB prior to the meeting with:

- Accrual totals entered into Velos
- Adverse event log reports for each study subject entered into the electronic data system
- Serious adverse event reports for each study subject entered into the electronic data collection system
- Study compliance issues if applicable
- The DSMB will also be provided each subject's study arm assignment by the primary biostatistician, [name].

The DSMB will define:

- All-cause mortality, with p-value to compare.
- Number, type, and severity of serious adverse events, overall and by treatment arm. No formal stopping rule is set for this comparison.
- Number of subjects in each treatment arm with at least one clinically documented infection leading to an ED or hospital admission with p-value. No formal stopping rule is set for this comparison.
- Unexpected adverse events and unanticipated problems overall and by treatment arm.
- Evaluate statistically significant difference in serious infection or pain admissions (**Section 10**) between the two arms.
- Recommend stopping guidelines as needed

9. SAFETY MONITORING AND STOPPING GUIDELINES

Interim monitoring plans and stopping guidelines will be defined by the DSMB. This section describes proposed plans. The study is expected to take three years to complete. Stopping guidelines are proposed for two outcomes, serious infection and pain crisis requiring ED or hospital admission. For these two outcomes, yearly looks at the data will take place. Therefore, three looks at the data (including the final look) are anticipated.

In designing the study, a serious infection difference of 20% between the 2 arms would be of clinical interest. As we do not expect to have adequate power in this study of 30 subjects to detect this difference, with an alpha of 0.05 with 15 in each arm, we will be able to detect an infection rate difference of 47-56% between the two arms. Any statistically significant difference in serious infection or pain admissions between the two arms will be considered as evidence for stopping the clinical trial.

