2. OBJECTIVES

2.1: Primary Aims

Note: This randomized clinical study should be considered a feasibility study to determine the ability to design and run a protocol of this nature. Each Aim was specifically selected

to maximize the possibility that novel information could be obtained from this trial. However, power calculations and associated precision estimates should be considered preliminary, as the data derived from this study will inform the calculations necessary to design a larger, more definitive study.

Aim 1:

To characterize the physiologic differences between ≥ 30 vs ≤ 10 day-old units. As part of the randomized study, we will measure PS exposure on donor red cells, as well as PE, microparticles, plasma free hemoglobin, heme, and NTBI. We hypothesize that ≥ 30 day-old units will have significantly more **biochemically old units** (see section 10 for the definition) than <10 day-old units. With a total sample size of 40 patients (20 in each group), we will have at least 80% power ($\alpha=0.05$) to detect a difference of at least 47% between the two randomized groups for biochemically old red cell units (close to a 100% difference is expected).

Aim 2:

To quantify whether physiologic differences between ≥ 30 day-old units versus ≤ 10 day-old units promote immune cell activation in transfused adults with SCD. We will perform flow cytometry to measure the activation of monocytes and neutrophils, as well as measure cell-free hemoglobin, heme and NTBI on blood samples before, 2, and 24 hours after transfusion. We hypothesize that those administered ≥ 30 day-old (biochemically old) units will have a greater increase in the number of CD62L + activated monocytes at 2 hours post-transfusion compared to those administered <10 day-old units. With a sample size of 40 patients, we will have 80% power ($\alpha=0.05$) to detect a change in MFI ratio of 1.35.

Aim 3:

To explore whether the physiology of ≥ 30 day-old units versus ≤ 10 day-old units is associated with adverse clinical outcomes in transfused adults with SCD. We will perform a systematic evaluation of hospital admissions, pain scores, medications, and clinical symptoms prior to each transfusion and at the end of the study period (**Table 1**). We hypothesize that reports of infection will be greater in subjects randomized to receive ≥ 30 day-old older units.

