10. STATISTICAL CONSIDERATIONS

10.1. Sample Size and Power

Participants will be recruited from UNC and Emory for this proposal. There are about 50 eligible patients at UNC and about 100 chronically transfused subjects at Emory. We anticipate no difficulties reaching our 40 patient study target. We anticipate that we will enroll at least 40 total individuals aged 16-60 years who are managed with chronic transfusions at UNC or Emory and will meet the study inclusion and exclusion criteria. This study will not attempt to stratify the study population for age or gender.

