The primary outcome measure is the change in CD62L (activated) circulating monocyte/macrophage MFI at 2 hours post-transfusion compared to the subject pre-transfusion. We will compare the two groups (\geq 30 day-old compared to \leq 10 day-old unit exposure) using a two sample two-sided t-test of the log at an alpha of 0.05. Power: We will have at least 80% power to detect a change in the ratio of 1.35 post-transfusion if the variability is similar to that seen in our preliminary data.

Exploratory: We will use a general(ized) linear model to include biochemically old units transfused (Aim 1 outcome), regardless of unit age, as a covariate in our analysis. Other co-variates in this model will include free heme, cell free hemoglobin, and NTBI. We will similarly compare other obtained activation measures as outcomes: activation markers for monocytes, neutrophils (as listed in section 6) and measured plasma cytokine

concentrations (section 6). We will also plan for auxiliary analyses of the outcome variables in which the explanatory variable is the age (days) of the RBC units --to characterize the degree to which age (days) can accurately predict the clinical and physiologic outcome measures defined. Lastly, as an exploratory aim, we will evaluate the *in vivo* change in recipient red cell PE/PS positivity at 2 and 24 hours post transfusion.

Aim 3:

The primary outcome variable is the rate of post-transfusion infections in the patient. The primary estimand is the treatment effect defined as the difference between the regimen-specific proportions of patients in the target populations that would experience post-transfusion infections. This population parameter will be estimated as a function of the proportions observed in the sample of patients studied. The point estimate will be reported along with the corresponding 95% confidence interval estimate. The presence of an indwelling catheter will be used as a key co-variate in this analysis. *Power:* A difference of 20% will be of clinical interest. We do not expect to have adequate power for this pilot study but at an alpha of 0.05 with 20 subjects in each group we will be able to detect a difference of 47% between the proportions.

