Exploratory: We will explore the relationship of blood age and transfusion of biochemically old red cell units on the change in Hb and HbS% over time, daily pain scores (0-10 as an ordinal scale), opioid use and dose, ED and hospitalization rate, infection symptoms, new alloantibody formation, and antibiotic use during the 3-month study period. We will compare groups using a Fisher exact test. We will also plan for auxiliary analyses of the outcome variables in which the explanatory variable is the age (days) of the RBC units --to characterize the degree to which age (days) can accurately predict the clinical and physiologic outcome measures defined.

AIM 4:

We will calculate the mean, median, minimum, and maximum levels of each metabolic compound analyzed by [name] in his laboratory at the University of Colorado. Analysis tools and methods will be determined by his research team, and will focus on changes in the patient and the unit pre and post transfusion.

AIM 5:

Feasibility Analysis: We will assess important variables necessary to develop a future larger clinical trial on this subject. Areas that we will investigate during the course of this trial will include frequency and content of missing data, subject drop out rates, and estimates of outcome measure precision. For this study, we will evaluate the number of males, females, and adolescents that enroll in the study to inform future studies. We do not expect there to be differences in the key outcomes based on these variables, and plan to analyze all 40 subjects together as one cohort, but differences by age and gender will be evaluated and considered.

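### Section 9 gives the trial size as 30 subjects (15 per arm) and the detectable infection difference as 47-56%, while the planned size everywhere else is 40 subjects (20 per group)

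*Combined protocol and SAP*

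**What the plan says.** Section 9 names a 20-point difference in serious infection as the difference of clinical interest. It then concedes that "we do not expect to have adequate power in this study of 30 subjects to detect this difference" and adds that, at an alpha of 0.05, "with 15 in each arm, we will be able to detect an infection rate difference of 47-56% between the two arms". It gives no power, test or baseline infection rate for that range.

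The other sections plan a larger trial:

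- The Synopsis sets recruitment, and the number randomized, at 40.
- Section 2.1 gives 40 patients for Aims 1 and 2, with 20 in each group for Aim 1.
- Section 10.1: "We anticipate no difficulties reaching our 40 patient study target".
- Section 10.2.1, Aim 1, repeats 40 patients and 20 per group, with at least 80% power for a difference of at least 47%.
- Section 10.2.1, Aim 3, on infection: "with 20 subjects in each group we will be able to detect a difference of 47% between the proportions".
- Section 10.2.1, Aim 5: the investigators "plan to analyze all 40 subjects together as one cohort".

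**The concern.** Section 9 and Section 10 describe trials of different sizes. They also give different detectable differences for infection: 47-56% at 15 per arm and 47% at 20 per group. Neither infection statement gives the assumptions that a reader would need to get from one to the other.

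Section 9 offers proposals for a DSMB that is to define the stopping guidelines itself. Section 8.6 asks the same board to evaluate serious infection and pain admissions by arm, and points to Section 10 when it does so. The board would therefore meet two sample sizes and two precision statements for one trial. What is at stake is whether it has a correct picture of how large an infection difference the completed trial could detect.

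**Working it through.** **1. Can the documents explain the 30?** Three explanations were considered.

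- *Evaluable number after losses.* Section 10.2 plans an intention-to-treat analysis of everyone randomized and anticipates no missing data or drop-outs.
- *Interim count.* Section 9 plans three yearly looks, including the final one, but ties the 30 to none of them and calls it the size of the study.
- *Low end of accrual.* The Synopsis has 15 already enrolled at Medical College of Wisconsin, 5-10 expected at UNC and 10-20 at Emory. 15 + 5 + 10 = 30 and 15 + 10 + 20 = 45, so 30 is the bottom of the projection. The same sentence still sets the goal at 40 randomized, and Section 9 does not call 30 a minimum.

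None of these reconciles the sections.

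**2. Inputs for the detectable difference.** From Section 9: n = 15 per arm, alpha 0.05. From Sections 2.1 and 10.2.1: n = 20 per group. Assumed, because Section 9 does not state them: Fisher exact test and 80% power (both borrowed from Aim 1), two-sided testing, and lower-arm infection rates scanned from 4% to 50%.

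**3. Formula.** For arm rates p and p + d,

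Power = Σₐ Σ_b Bin(a; n, p) · Bin(b; n, p + d) · 1[Fisher P-value for a/n against b/n ≤ 0.05].

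The detectable difference is the smallest d, in steps of 0.001, with power of at least 0.80.

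**4. Results, in percentage points at 80% power.**

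| Lower-arm rate | 15 per arm | 20 per arm |
|---|---|---|
| 4% | 47.3 | 37.8 |
| 5% | 48.7 | 39.1 |
| 10% | 53.5 | 42.9 |
| 20% | 55.8 | 47.3 |
| 25% | 55.8 | 48.3 |
| 40% | 52.1 | 45.2 |
| 50% | 46.6 | 41.8 |
| Range over 4-50% | 46.6-55.9 | 37.8-48.3 |

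The plan's own figure reproduces: 46.6-55.9 rounds to 47-56. Over the same rates, 20 per arm gives 37.8-48.3. Below 4% the figures fall further: at 0% they are 40.8 for 15 per arm and 31.4 for 20 per arm.

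**5. Aim 3's 47%.** At 20 per arm the calculation gives 47.3 points at a lower-arm rate of 20%, where power for exactly 47 points is 79.5%. So 47% is attainable at 20 per group under these assumptions, near that one baseline rate. At 15 per arm and the same rate, power for 47 points is 61%. The 47 in both sections therefore need not be the same calculation.

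**6. Power for the 20-point difference of interest** (lower-arm rates 0-50%): 9.5-16.9% at 15 per arm and 14.3-37.0% at 20 per arm.

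**The case against.** The strongest case is that this is editorial. Section 9 labels its content as proposals and leaves the guidelines to the DSMB. Section 2.1 calls the study a feasibility study with preliminary power calculations. The proposed trigger is any statistically significant difference between arms, which does not use 47-56%. The admission of inadequate power for 20 points is true at 30 or 40 subjects. The stated range is mostly conservative for 40. All of this stands, and it keeps the consequence small. It does not make the text right: preliminary describes uncertain estimates, not a planned sample size that contradicts the rest of the protocol.

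Three stronger readings are tempting and are not supported.

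- *That 56 points could never be the detectable difference with 20 per arm.* This depends on a power that Section 9 does not give. At 20 per arm the maximum is 48.3 points at 80% power and 54.1 at 90%, but 58.6 at 95%.
- *That 47-56% is a serious-infection figure, so Aim 3 concerns a different outcome.* Section 9 calls the 20-point difference serious, but attaches 47-56% only to an infection rate difference. For Aim 3, "The primary outcome variable is the rate of post-transfusion infections in the patient". Section 6.8 defines acute infection as needing medical facility intervention, and Section 8.6 counts subjects with "at least one clinically documented infection leading to an ED or hospital admission" while referring serious infection to Section 10. The documents neither equate these outcomes nor clearly separate them. For the same reason, Aim 3's 47% should not simply be copied into Section 9.
- *That the stopping proposal was sized for the wrong trial.* The trigger has no sample-size input. A calculation at full enrolment and single-look alpha also says nothing about what the earlier yearly looks could detect.

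**Conclusion.** The contradiction of 30 with 40 subjects, and of 15 with 20 per arm, is plain from the text and needs no assumption. That 47-56% belongs to the smaller trial is an inference. It rests on an assumed two-sided Fisher test, 80% power and lower-arm rates of 4-50%, under which the range is reproduced at 15 per arm and becomes about 38-48 points at 20 per arm. A reader might suppose that Section 9 was carried over from a 30-subject plan; that is plausible, but the documents do not say so.

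The point is worth correcting but minor. It affects what Section 9 tells the DSMB about the size and sensitivity of the trial. No decision rule in the plan is shown to depend on it.

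**What to change.** In Section 9, change 30 subjects to 40 and 15 in each arm to 20. Replace 47-56% with the sponsor's own detectable difference for 20 per arm, stating the power, test, baseline rate and infection outcome behind it, and say how it relates to the 47% given for Aim 3 in Section 10.2.1. The 38-48 point range above is an illustration, not proposed protocol text. If 30 is intended, for example as an evaluable number, state that and explain it.

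Separately, and only as a query: Section 10.1 describes the 40 as managed at UNC or Emory, while the Synopsis appears to count the 15 enrolled at Medical College of Wisconsin towards the goal. The sponsor could confirm whether the 40 include those 15.

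The cost is a few words and one short recalculation. Randomization, the recruitment target, the stopping trigger and the analyses do not change.
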